In two large Maryland healthcare systems, fewer than 5% of persons with schizophrenia who smoke are prescribed evidence-based smoking cessation pharmacotherapy;^{13,14} limited available research shows similarly low rates in other states.^{12,15} Rates of behavioral smoking cessation counseling are also low.¹⁶ As many people with SMI receive the majority of their healthcare in the specialty mental health sector,¹⁷⁻¹⁹ it is critical to increase mental health providers' delivery of evidence-based smoking cessation treatment. Strategies to achieve this goal will need to overcome knowledge and self-efficacy barriers among mental health providers, including skepticism that people with SMI want to quit smoking, misperceptions about cessation treatment efficacy and safety for this group, and low self-efficacy to deliver evidence-based smoking cessation treatment for consumers with SMI.^{12,20-23} Mental health providers may also perceive smoking cessation treatment as outside their scope of practice.^{12,20-23} Clinic-level barriers to treatment, such as lack of systems for assessing smoking status and willingness to quit among consumers with SMI, may also need to be addressed.^{20,21} No published studies have evaluated implementation strategies to increase mental health providers' delivery of evidence-based smoking cessation pharmacotherapy and counseling for people with SMI.

This is a R34 pilot study funded by NIMH as part of the Johns Hopkins NIMH P50 Center to Accelerate Translation of Interventions to Decrease Premature Mortality in Series Mental Illness. This is a pilot study to assist and study the implementation of evidence-based smoking cessation treatment in community mental health clinics in Maryland over 12 months. In this study, we will develop and test an implementation intervention designed to improve mental health providers' knowledge, self-efficacy and delivery of evidence-based smoking cessation treatment. The implementation intervention includes both synchronous and asynchronous training modules, including using an avatar practice module for motivational interviewing skills, a tobacco smoking identification and cessation protocol, expert consultation, coaching and organizational strategy meetings. The study is guided by Gurses et al.'s interdisciplinary framework of clinicians' compliance with evidence-based guidelines.²⁴

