Persons with serious mental illness (SMI) have a mortality rate three times higher than those without SMI,^{2,25-27} primarily due to cardiovascular disease (CVD),²⁸⁻³¹ and tobacco smoking is the single largest contributor to CVD and premature mortality in this population.^{1,2} Fifty-three percent of US adults with SMI smoke tobacco,³ compared to 15% of US adults overall.⁴ Smoking prevalence is highest among adults with schizophrenia, with estimates of >60%.³² Smoking cessation has significant benefits: after one year of abstinence from tobacco smoking, risk of myocardial infarction is reduced by 50%, and smoking cessation in mid-life eliminates 90% of smoking-related mortality risk.^{33,34} Combination pharmacotherapy (3 efficacious options are available: varenicline, bupropion or nicotine replacement therapy (NRT)) and behavioral counseling is effective cessation treatment for smokers with SMI,⁷⁻¹⁰ but estimates suggest that fewer than 5% of smokers with SMI receive pharmacotherapy,¹²⁻¹⁵ and rates of behavioral counseling – which, alone, is not effective cessation treatment for smokers with SMI¹⁰ – are also low (≈12%).¹⁶

Research shows modifiable knowledge and self-efficacy barriers to mental health providers' delivery of evidence-based smoking cessation treatment.^{12,20-23} While 65-80% of smokers with SMI want to quit,⁶ in a recent study 77% of mental health providers believed smokers with SMI are not interested in quitting.²² Providers' disproven but persistent concerns that cessation may increase SMI symptoms and/or disrupt psychotropic medication regimens and their uncertainty about the safety of smoking cessation pharmacotherapy may also impede treatment.^{12,22} In 2009, case reports³⁵⁻³⁷ of adverse psychiatric side effects led to black box warnings on varenicline and bupropion. These warnings were removed in December 2016 after cohort and clinical trial evidence showed no increased risk of adverse psychiatric events among people with SMI.^{8,13,14,38} While few mental health providers feel comfortable delivering cessation treatment, they report high willingness to do so if they were to receive training.²² Mental health clinic-level barriers, including lack of systems for assessing and tracking consumers' smoking status and willingness-to-quit, may also need to be addressed.^{20,25}

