Study sites and participants: We plan for five community mental health clinics in Maryland to participate in this study. The clinics serve populations with serious mental illness. Participants for data collection and the implementation intervention will be employees of the community mental health organization including leaders, mental health providers (psychiatrists and/or nurse practitioners, licensed counselors, psychologists, social workers), primary care providers and other staff. We estimate N=120 employee participants across the five sites. Employees may take part in different parts of data collection, depending on their role in the clinic. Patients with serious mental illness seen in the clinic are also study participants as their data will be analyzed.

Description of Implementation Intervention: The multicomponent implementation intervention is designed to improve providers' knowledge, self-efficacy and delivery of evidence-based smoking cessation treatment for smokers with SMI. The intervention includes training on evidence-based smoking cessation treatment, including an innovative online avatar motivational interviewing practice module; a tobacco smoking identification and cessation protocol; expert consultation for prescribers and therapists; coaching; and organizational strategy meetings. A more detailed description of each component is outlined below.

Tobacco smoking identification and cessation protocol: Our team has developed a tobacco smoking identification and cessation protocol to assist providers in delivering evidence-based smoking cessation treatment. This protocol includes a resource guide that provides an overview of the IMPACT study and will help clinicians navigate their work on the project, a manual for delivering smoking cessation behavioral counseling sessions and pharmacotherapy, and willingness-to-quit guides to help facilitate brief smoking cessation conversations based on patient responses to the tobacco smoking status and willingness-to-quit assessment.

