Fidelity to Motivational Interviewing: Standardized Actor Interviews will be conducted to assess fidelity to motivational interviewing.	All providers (~25 per site)	30 minutes		3, 6, 12 months
Fidelity to behavioral smoking cessation counseling: Standardized Actor Interviews will be conducted to assess fidelity to smoking cessation behavioral counseling sessions				
Smoking and Smoking-Cessation Measures				
These are our primary measures of fidelity to evidence-based smoking cessation treatment.	All mental health consumers (patients) (~3000 per site)			Baseline through 12 months
Guideline-concordant smoking cessation treatment: Measures will be calculated at site & provider levels				
Smoking status assessment rates: % of visits where smoking status assessment is documented.				
Willingness-to-quit assessment rates: % of visits where willingness-to-quit assessment is documented.				
Prescription Rates: % of willing-to-quit smokers prescribed, or offered but refused, cessation pharmacotherapy. ²				
Behavioral Counseling Rates: (1) % of not willing-to-quit				

smokers given brief behavioral counseling to increase willingness-to-quit; and (2) % of willing-to-quit smokers who were referred to the clinic's cessation counselor. ² Among willing-to-quit smokers referred the counselor, we will also measure the number of counseling sessions completed.			
7-day abstinence: % of willing-to-quit consumers abstinent for ≥ 7 days self-report, documented in the EMR	All mental health consumers (patients) (~3000 per site)		Baseline through 12 months
Other Patient Measures Year of birth, gender, race/ethnicity, primary mental health diagnosis, hospitalization during the study period	All mental health consumers (patients) (~3000 per site)		Baseline through 12 months

Qualitative Data Collection

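### The prescription and referral rates are taken over smokers documented as willing to quit, a group the intervention itself should enlarge, so their change from baseline to 12 months can be biased in size or direction.

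*Combined protocol and SAP*

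**What the plan says.** The overview in Section 4 names four practices as the main outcome: screening for tobacco use, assessing willingness to quit, behavioral counseling and pharmacotherapy. The last two are meant for patients interested in cutting down or quitting.

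Table 2 turns these into rates:

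- Pharmacotherapy: "Prescription Rates: % of willing-to-quit smokers prescribed, or offered but refused, cessation pharmacotherapy".
- Referral: the percentage "of willing-to-quit smokers who were referred to the clinic's cessation counselor".
- Assessment, over a different unit: "Willingness-to-quit assessment rates: % of visits where willingness-to-quit assessment is documented".

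Seven-day abstinence has the same type of denominator as the two treatment rates (the percentage "of willing-to-quit consumers abstinent for ≥ 7 days self-report, documented in the EMR"). This point concerns the treatment rates only.

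In Section 4, the guides for providers work from "patient responses to the tobacco smoking status and willingness-to-quit assessment", so willingness is known from that assessment. Aim 2 in Section 2 lists the assessment among the practices to be increased. Section 3 gives as a possible clinic barrier the "lack of systems for assessing and tracking consumers' smoking status and willingness-to-quit".

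Section 7a compares baseline with 12 months in multi-level models. It does not say how smokers with no documented willingness are handled.

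**The concern.** A before-after comparison of a rate is easy to read when the same kind of patient is in the denominator both times. Here a smoker seems to enter the denominator only after being asked, and asking is something the intervention promotes. If few smokers are asked at baseline, those few may be the ones a provider was already about to treat. If many more are asked at 12 months, the denominator takes in smokers who would earlier have been left out altogether.

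The measured change then mixes two things: how many more smokers are treated, and how many more are asked. A clinic that treats more smokers could show a smaller gain than it achieved, or even a decline. Section 1 says the results will inform the design of a large-scale trial, so a misleading signal on prescribing or referral would carry forward.

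**Working it through.** The plan gives no expected rate or sample size for these measures (Section 7c is marked not applicable), so there is no figure to reproduce. The check asks when the planned rate moves against the number treated.

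**Inputs from the protocol.** About 3,000 patients per site (Table 2); 53% smoke, 65-80% of smokers want to quit, and fewer than 5% of smokers receive pharmacotherapy (Section 3). The Abstract gives a similar local figure, for two Maryland healthcare systems: "fewer than 5% of persons with schizophrenia who smoke are prescribed evidence-based smoking cessation pharmacotherapy". I use 5%.

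**Assumed inputs.** Share of smokers assessed: a0 = 10% at baseline, a1 = 80% at 12 months. Prescribing grows by m = 3. A share s = 50-75% of baseline prescriptions falls among smokers documented as willing, and all of them do at 12 months. The willing share w is the same at both times. No declined offers are counted.

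**Counts per site.** Smokers: 3,000 × 0.53 = 1,590. Prescribed at baseline: 1,590 × 0.05 = 79.5. Prescribed at 12 months: 3 × 79.5 = 238.5.

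**Planned rate** = numerator / (1,590 × a × w).

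- Baseline, low end: 0.50 × 79.5 / (1,590 × 0.10 × 0.80) = 39.75 / 127.2 = 31%.
- Baseline, high end: 0.75 × 79.5 / (1,590 × 0.10 × 0.65) = 59.6 / 103.35 = 58%.
- 12 months: 238.5 / (1,590 × 0.80 × 0.80) = 238.5 / 1,017.6 = 23%, to 238.5 / (1,590 × 0.80 × 0.65) = 238.5 / 826.8 = 29%.

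The planned rate falls, while prescribing per 100 patients rises from 79.5 / 3,000 = 2.65 to 238.5 / 3,000 = 7.95.

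**Break-even.** The rate falls when s / a0 > m / a1, that is, when a0 < s × a1 / m. The 5% and the willing share cancel, so the direction does not depend on them.

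| Growth in prescribing (m), with a1 = 80% | s = 50% | s = 75% |
|---|---|---|
| 2 | 20% | 30% |
| 3 | 13% | 20% |
| 4 | 10% | 15% |

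Each cell is the baseline share assessed below which the planned rate falls.

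**A rise can also be distorted.** With a0 = 30% and m = 3, the baseline rate is 39.75 / (1,590 × 0.30 × 0.80) = 10% to 59.6 / (1,590 × 0.30 × 0.65) = 19%, against 23-29% at 12 months. The rate ratio is 3 × 0.30 / (0.80 × s) = 1.5 to 2.25, although prescribing tripled.

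**A second set of assumptions.** If all baseline prescriptions are in the documented-willing group, w = 65% and a1 = 70%, the break-even is 0.70 / 3 = 23%. The rate goes from 38.5% to 33.0% if 20% were assessed at baseline, and from 25.6% to 33.0% if 30% were.

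**Declined offers.** Table 2 counts them in the numerator. With a0 = 10% and a1 = 80% the denominator grows 8-fold, so the fall vanishes once the 12-month numerator reaches 8 × 39.75 = 318 to 8 × 59.6 = 477. That takes about 80 to 239 declined offers on top of 238.5 prescriptions, if there were none at baseline.

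**Per-visit assessment rates.** Asking every smoker once a year gives 1/4 = 25% of smokers' visits at four visits a year, but 1/12 = 8.3% at twelve (visit counts assumed). A per-visit rate therefore cannot be converted into the share of smokers assessed.

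**The case against.** The best defense is that the practice is defined for patients interested in cutting down or quitting, so willing smokers are the natural denominator for guideline-concordant care. That stands, and it is why the conditional rates should stay. It does not make them a clean before-after contrast.

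Second, assessment has its own rates among the main outcomes. A reader might infer that the plan rewards a clinic for asking only those it already means to treat. The documents do not support that: such a clinic would do badly on the willingness rate. The safeguard is only partial, because that rate is per visit.

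Third, the baseline picture is uncertain. Section 3 says lack of systems may need to be addressed; it reports no rate for these clinics. Section 4 says they already provide some cessation treatment, and it does not say whether baseline data come from existing notes or from first entries on new forms. Selective asking at baseline is plausible but not shown.

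Fourth, the exclusion of unassessed smokers is inferred from the denominator. Both treatment definitions carry a superscript 2 whose text is not visible, and the separate medical record variables document is not included. Either could contain a rule.

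Fifth, training prescribers in these conversations should raise documented offers, which works against any fall.

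**Conclusion.** The concern holds in a limited form. The denominator of the prescription and referral rates depends on an assessment that the intervention targets, no visible rule covers unassessed smokers, and the per-visit rates cannot correct for the shift. The change from baseline to 12 months can therefore be wrong in size, and under some conditions in direction.

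A reader might infer that the plan will report worse prescribing when prescribing improves, or that the willing-to-quit rates must be replaced. Neither follows. With prescribing tripled and 80% assessed at 12 months, the fall needs baseline assessment below about 13-20% of smokers and few documented declined offers. The 10%, 80%, tripling and 50-75% figures are all assumptions. What is established is that the change cannot be interpreted without a per-patient assessment share, which Table 2 does not include. For a pilot, this is a should-fix.

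**What to change.** Keep the willing-to-quit rates. In Table 2 and Section 7a, prespecify beside them for the comparison of baseline with 12 months:

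- patients prescribed cessation pharmacotherapy, or offered it and declining, and separately patients referred for counseling, each per 100 patients seen in equal windows;
- the per-patient share with smoking status documented, and with willingness documented, at each time point.

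State how a smoker with no documented willingness is counted, and that a change in the conditional rates will be interpreted only alongside these companions.

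The cost is mainly in definitions: Table 2 already covers all patients and visits at each site and already needs the prescribing and referral counts. Availability must still be confirmed. Section 4 names medication and outpatient-encounter data only for the Johns Hopkins site. The content of the record transfers from other sites is not listed, and one site plans a deidentified spreadsheet. Each of these sites should confirm that it can supply the counts.

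There are two downsides. The companion percentages are smaller, because they include non-smokers and unwilling smokers. They can also rise from better documentation alone, so they complement the planned rates and do not replace them.

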The study will result in a set of training and implementation tools and resources for community mental health clinics to address tobacco smoking. Results also will inform the future design of a large-scale trial testing strategies to increase delivery of evidence-based smoking cessation treatment for SMI in community mental health settings.

2. Objectives

The specific aims are:

Aim 1: To inform implementation intervention development, examine barriers to evidence-based smoking cessation treatment in community mental health clinics serving consumers with SMI.

1. What do providers in a community mental health organization perceive as the key barriers to delivery of evidence-based smoking cessation treatment, and what strategies could help to overcome these barriers?

Aim 2: Assess the implementation intervention's effects on providers' knowledge, self-efficacy, and delivery of evidence-based smoking cessation treatment and preliminary measures of consumers' abstinence from tobacco smoking. The intervention will:

1. Increase providers' knowledge of smoking cessation treatment for consumers with SMI.
2. Increase providers' self-efficacy to deliver evidence-based smoking cessation treatment.
3. Increase providers' delivery of the four key components of evidence-based smoking cessation treatment: assessment of smoking status & willingness-to-quit, pharmacotherapy prescribing, and behavioral counseling.
4. Increase abstinence from tobacco smoking among consumers with SMI.

Aim 3: Assess the acceptability, appropriateness, and feasibility of the implementation intervention to increase delivery of evidence-based smoking cessation treatment:

1. The implementation intervention will be perceived as acceptable, appropriate, and feasible by community mental health clinic providers.

3. **Background** (briefly describe pre-clinical and clinical data, current experience with procedures, drug or device, and any other relevant information to justify the research)

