Few mental health providers deliver evidence-based smoking cessation treatment and many mental health clinics lack standard systems for screening, monitoring, and treating tobacco smoking.^{12,22} Community mental health settings are often under-resourced and providers face multiple competing demands and smoking cessation has not historically been an organizational priority. As noted above, mental health providers may face knowledge and self-efficacy barriers that impede their delivery of evidence-based smoking cessation treatment.^{12,20-23} Nonetheless, mental health providers' extensive experience working with consumers with SMI makes them optimally positioned to deliver effective cessation treatment for tobacco smoking, the leading cause of premature mortality among people with SMI.

4. Study Procedures

- a. Study design, including the sequence and timing of study procedures (distinguish research procedures from those that are part of routine care).
- b. Study duration and number of study visits required of research participants.

Currently this protocol is being submitted as a study where all study procedures are delivered remotely. If and when COVID-19 restrictions are lifted, we may submit a petition to have some of the study activities in-person as appropriate.

Overview: We will work with 5 community mental health clinics in Maryland. This project's goal is to implement evidenced-based tobacco smoking cessation treatment in community mental health clinics serving the population of persons with serious mental illness. Tobacco smoking cessation treatment involves behavioral counseling and pharmacotherapy. The main outcome of the project is the utilization of 4 evidence-based practices in the clinic setting: 1) screening for tobacco use in all patients, 2) an assessment of willingness to quit for those who smoke, 3) referral and utilization of behavioral counseling for those interested in cutting down or quitting smoking, 4) receipt of pharmacotherapy for those interested in cutting down or quitting smoking. The community mental health clinics are already providing some treatment for smoking cessation for their patients. The evidence-based practices in this project are within their scope of practice. The implementation intervention is 12 months.

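### Aim 2.4 targets abstinence among consumers with SMI, but the only measure is a percentage of willing-to-quit consumers, a group the intervention can change unless it is fixed beforehand

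*Combined protocol and SAP*

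**What the plan says.** - Section 2, Aim 2, item 4 reads "Increase abstinence from tobacco smoking among consumers with SMI". It has no restriction by willingness. The lead-in to Aim 2 calls these "preliminary measures of consumers' abstinence from tobacco smoking".
- Section 4, Table 2, gives one abstinence measure: "7-day abstinence: % of willing-to-quit consumers abstinent for ≥ 7 days self-report, documented in the EMR". Its timing is "Baseline through 12 months". The column for who is measured lists all patients, about 3000 per site. That says whose records are used; the percentage is still taken among willing-to-quit consumers.
- The Overview in Section 4 names "an assessment of willingness to quit for those who smoke" as one of the four practices whose use is the main outcome. Table 2 counts this assessment per visit, so one patient's status can be recorded more than once.
- Table 2's counseling row covers not-willing "smokers given brief behavioral counseling to increase willingness-to-quit".
- Section 7a compares baseline with 12 months for abstinence in a multi-level model and speaks of intervention effects. It defines no analysis set for this outcome.
- The end of the Abstract says "Results also will inform the future design of a large-scale trial".

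**The concern.** The measure is narrower than the aim, and the restriction is not neutral. The intervention acts on the willing-to-quit group in two ways: it prompts providers to ask about willingness, and it asks them to counsel not-willing smokers so that they become willing. If membership is updated over the 12 months, success at either step changes who is counted.

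The later denominator may then hold smokers with a different chance of quitting from those counted at baseline. The reported rate could fall or stay flat while more smokers quit, or rise because of who is recorded. Abstinence is the only aim stated as a change in patients' smoking, and the pilot is meant to feed the design of a larger trial, so a rate distorted in this way could mislead that design.

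**Working it through.** The plan states no expected abstinence rate, sample size or power, so there is no figure of its own to reproduce. The calculations below only show what a moving denominator can do.

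**Inputs.** Section 3 says 65-80% of smokers with SMI want to quit. The two ends are used here as *assumed* before and after shares of smokers classed as willing; the protocol does not present them as a change over time. All quit rates are assumptions. Smokers who stay unwilling are assumed to quit at 0%.

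**1. Willingness rises.** Let w be the willing share after, a the abstinence rate among the already willing after, and q the rate among the newly willing.

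- Table 2 measure after = (0.65 × a + (w − 0.65) × q) / w
- All-smoker abstinence after = 0.65 × a + (w − 0.65) × q
- Before, with the already willing at 5%: measure 5.00%; all smokers 0.65 × 5% = 3.25%

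| w | a | q | All smokers after | Table 2 measure after |
|---|---|---|---|---|
| 0.80 | 5% | 1% | 3.25 + 0.15 = 3.40% | 3.40 / 0.80 = 4.25% |
| 0.80 | 5% | 5% | 3.25 + 0.75 = 4.00% | 4.00 / 0.80 = 5.00% |
| 0.80 | 5% | 9% | 3.25 + 1.35 = 4.60% | 4.60 / 0.80 = 5.75% |
| 0.80 | 6% | 1% | 3.90 + 0.15 = 4.05% | 4.05 / 0.80 = 5.06% |
| 0.70 | 5% | 1% | 3.25 + 0.05 = 3.30% | 3.30 / 0.70 = 4.71% |

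The first and last rows show a reversal: the measure falls while all-smoker abstinence rises. It depends on the already willing not improving. With w = 0.80 and q = 1%, the measure is back at 5.00% when 0.65 × a + 0.15 = 4.00, that is, a = 3.85 / 0.65 = 5.92%. With w = 0.70, the break-even is (3.50 − 0.05) / 0.65 = 5.31%.

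**2. Only recording changes.** Suppose nobody's smoking changes, the share of smokers recorded as willing goes from 30% to 65%, and those recorded first are 5% abstinent. The measure starts at 5.0% and becomes (0.30 × 5% + 0.35 × q) / 0.65, where q is the rate among those recorded later:

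- q = 1%: 1.85 / 0.65 = 2.8%
- q = 3%: 2.55 / 0.65 = 3.9%
- q = 5%: 3.25 / 0.65 = 5.0%
- q = 7%: 3.95 / 0.65 = 6.1%
- q = 9%: 4.65 / 0.65 = 7.2%

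True abstinence is the same before and after in every line, yet the measure can move either way.

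**3. Why the replacement needs documentation shares.** Take a constant true rate of 5%, with documentation unrelated to abstinence. If documentation rises from 10% to 90%, counting undocumented patients as not abstinent moves the rate from 0.05 × 0.10 = 0.5% to 0.05 × 0.90 = 4.5%, while the rate among the documented stays at 5.0%. If abstinent patients are twice as likely to be documented, the rate among the documented reads 0.10 / (0.10 + 0.95) = 9.5%. Neither version is safe alone.

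**The case against.** Willing-to-quit smokers are those to whom the Overview directs cessation counseling and pharmacotherapy, so they are a natural denominator for a treatment cascade. The main outcome is use of four practices, and abstinence is labelled preliminary in a pilot. All of this stands. It supports keeping the measure and limits severity, but it does not make the measure answer Aim 2.4.

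The timing of classification may be defined in the medical record variables document cited in Section 4, which is not among the documents here. A table note may also have been lost: the prescribing and counseling rows carry a superscript 2, though the abstinence row does not. A reader might infer that the plan uses a rolling group. The text is compatible with that but does not say it.

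A reader might also infer that the measure will understate the intervention, or that it reverses whenever newly willing smokers quit less often than the already willing. Neither follows. The reversal shown needs little or no improvement among already-willing smokers, the group to whom treatment is directed, and the recording example runs both ways.

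Finally, if the group is fixed at baseline, one might object that background quitting would be read as an effect. That is the general weakness of a design without a control. The proposed all-smoker measure shares it, so it is no argument for one denominator over the other.

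**Conclusion.** The point holds in a conditional form. On the visible text, the only abstinence measure is narrower than Aim 2.4 and is conditioned on a status that the intervention sets out to assess more often and to change. That mismatch remains whatever the timing. If willingness is not fixed before the intervention, the denominator can also move with it, and the measure can then diverge from abstinence among all smokers in either direction.

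The size cannot be derived from the documents. Under the assumed rates, the divergence ranges from a fall of 0.75 points in the measure against a rise of 0.15 points among all smokers to a rise in both. Recording changes alone could move a 5.0% rate to anywhere between 2.8% and 7.2%. This should be fixed, with medium confidence; the pilot setting and the preliminary label keep it from being more serious.

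**What to change.** 1. For Aim 2.4, add 7-day abstinence among all patients documented as current smokers at the start of the period, regardless of willingness.
2. Keep the willing-to-quit rate as a treatment-cascade measure, and state when willingness is classified and whether it is updated.
3. For each period, report the share of patients with smoking status documented and the share of those smokers with follow-up abstinence documented. Show abstinence both among those documented and with undocumented counted as not abstinent.
4. Describe the result as a pre/post change, not as an effect of the intervention.

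The prescribing rate, a percentage "of willing-to-quit smokers prescribed, or offered but refused, cessation pharmacotherapy", and the referral rate have the same conditioning. All-smoker versions could be tabulated as a supplement.

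The cost is a lower headline percentage, some extra tabulation, and a stable patient ID at the site that plans a deidentified spreadsheet. Some recording tools were built for this project, so comparable baseline data may not exist. In that case only a 12-month rate can be given, with an interval that allows for clustering in a handful of clinics, and it will be imprecise. The change reduces the bias but does not remove it: documented smoking status is itself affected by the intervention, and there is no control.
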